We will recruit individuals (n=138) with lung cancer over a 2.5 year period using a similar approach that we used for our NRI pilot study. We will target recruitment activities to identify all patients at both VA PSHCS and Alabama VA with lung cancer who will receive therapy other than solely surgical resection. Virtually all patients undergoing evaluation for lung cancer at the both VAs are presented at the Tumor Board, or are evaluated in the chest (thoracic surgery and pulmonary), oncology and radiation oncology clinics. As members who regularly attend the tumor board, we are well acquainted with other Tumor Board attendees, including physicians, social workers, and other support staff. Each week, we will review patients who are to be presented at Tumor Board, or seen in the Chest (includes pulmonary and thoracic surgery) and Oncology Clinics for patients with new diagnoses of lung cancer.

We will mail potential candidates invitation letters and include pre-paid postcards providing an opportunity for patients to opt out of the study or to be contacted if they are interested in learning more about the study. We will contact patients initially by telephone to introduce the study. Among interested patients, we will take two approaches to obtain informed consent and conduct the initial study visit based on patient preference. First, if the patient has an upcoming clinical appointment, we will coordinate the initial study visit with that clinic visit. Second,

because of the travel and clinical burden, we will also offer to perform the informed consent process and initial interviews by telephone. For several of our pilot studies we have conducted informed consent over the telephone and have not experienced any unforeseen challenges. Given the frequency at which patients are seen in clinics, we anticipate that the majority of these initial interviews will be performed in person. If a patient elects to participate in this study, we will document this in the medical record to inform all medical providers of their patients' involvement.

Patients will receive \$50 following randomization into the study, \$25 after completing 8 weeks in the study and \$25 after completion of the final assessment for a possible total of \$100.

Measures

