Outcome measures will be collected on all enrolled participants by a research coordinator at baseline and the final visit. Outcome measures will be collected through surveys over the telephone. Prior to data collection, we will mail the surveys to the patient so they can visually follow while the research coordinator asks the questions and records their response. The estimated time for completion of the six surveys is approximately 30-45 minutes based on our pilot study. Subjects did not commonly report being overly burdened by the surveys.

C. Method of randomization

The unit of randomization will be the patient, performed at a ratio of 1:1 within strata using the permuted-block method with block sizes of 4 [3]. Given three stratifying variables of cancer stage (early and late), site (Seattle, Birmingham, Portland) and COPD (yes or no), there will be eight strata. Patients from each strata will be assigned to the intervention (I) or the control (C) in randomly generated sequences ICIC, IICC, CIIC, and so forth as they enter the trial.

Randomization will be conducted by a statistician on our study team. Providers will not be specifically informed of patients' treatment allocation. However, providers cannot be masked in this intervention trial and will have access to the research notes entered into CPRS by the study nurse. The research coordinator collecting baseline and final visit outcome measures will be blinded to the subject's treatment allocation.

D. Interim analysis of the data

Stopping rules

There are no formal stopping rules for safety, efficacy, and futility for the study. This determination was made based on previous studies incorporating palliative care interventions into routine care finding improvements in quality of life and depression for patients with advanced cancers. ER visits, hospitalizations, and death are expected for patients with advanced cancers. These events are due to the underlying disease or side effects from cancer treatments, not from a palliative care intervention. This study does not involve investigational medications or devices. Patients will continue to receive standard of clinical care for their lung cancer during the study.

During our pilot study, no complaints were received from study participants regarding the study procedures and there were no reported unanticipated serious adverse events due to study participation. Therefore, the study's sample size should not be impacted.

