For secondary aim 1, we will evaluate if the intervention is associated with higher satisfaction of care as measured by FAMCARE-P. The evaluation of this aim will take the same form as that described for FACT-L TOI above including multiple imputation and sensitivity analyses.

For secondary aim 2, we will assess if the intervention makes a difference in patient activation to discuss their treatment preferences with their provider from baseline to the final visit. Item responses on the Health Care Communication Questionnaire are ordinal. We will use Wilcoxon rank sum test [6] to analyze the change in the score from baseline to the final visit.

For secondary aim 3, we will assess if the intervention will make a difference in improving the level of concordance between the clinicians' knowledge of the patients' life-sustaining treatment. Item responses for these questions are ordinal. We will use Wilcoxon rank sum test to analyze the difference between the subjects' and providers' responses.

For secondary aim 4, we will determine if the provision of palliative care integrated at the time of lung cancer diagnosis improves appropriate resource utilization (pharmacy, social work, dietician, spiritual care, psychology, and PT/OT) as compared to the usual care group. We will collect data on health care utilization from CDW at the end of the study period (3 years). Measures include: 1) number of hospital admissions (for any reason); 2) number of intensive care admissions; 3) use of mechanical ventilation or no use of mechanical ventilation; 4) the number of Emergency Department visits (for any reason); 5) number of cancer treatments (chemotherapy); 6) number of radiation treatments—definitive or curative; 7) fee service for hospice care; and 8) survival status. Referrals to system interdisciplinary resources (pharmacy, social work, dietician, spiritual care, psychology, and PT/OT) will be monitored on a monthly basis for all enrolled subjects.

G. Prospective tracking of serious adverse events

Data and Safety Monitoring Board

An external and independent data safety monitoring board (DSMB) will be established to examine interim study results on a periodic, scheduled basis and to recommend early termination due to the burden of participation if warranted. The issues that are raised in these interviews bring up sensitive subjects among a terminally ill group of patients and it is

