reasonable to expect that the surveys may cause some patients distress. If patients have any questions or do not feel comfortable responding to specific survey questions, they have the right to refuse and will be informed of their right to opt out of any questions.

Specifically, we propose that the data safety monitoring board to assess and respond to complaints and monitor all deaths and hospitalizations.

If depression or suicidal ideation or intention is detected during the phone conversations, study staff will adhere to the VA suicide protocol.

During the administration of the study questionnaires and during the intervention telephone calls, study staff may detect symptoms of depression. If this situation occurs, we will inform the Primary Care Physician and refer the patient to Mental Health services for further evaluation. In the unlikely but possible detection of suicidal ideation, the following protocol will be followed:

The interviewer will ask, "You mentioned that you have had thoughts that you would be better off dead or hurting yourself in some way. Do you have a plan for how you would hurt yourself?" If the subject says: "I would not actually hurt myself", the interviewer may continue with the interview. If the subject endorses a plan, the interviewer would proceed as follows: "Our highest priority is keeping Veterans safe. I would like to have one of our study doctors call you to make sure you are safe."

If the Veteran indicates he/she is safe, but does not want to be evaluated by a study doctor or mental health provider, let him/her know you will need to contact the mental health provider to ensure his/her safety. In the case of possible suicidal intention or ideation, the Veteran will be provided with the VA Suicide Hotline number.

If the Veteran indicates he/she will wait for an evaluation from the study doctor or mental health provider, thank him/her and let him/her know that a doctor will be seeing him/her soon. Then call the mental health provider/study doctor to see the Veteran and assess his/her suicidality.

DSMB Role

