The DSMB will provide the investigators and the IRBs with objective, scientific monitoring of the conduct of the study from the standpoint of ensuring the protection of human subjects and the integrity of the trial. It will do so by regularly monitoring adverse events (AEs) and serious adverse events (SAEs) and the quality of data, as well as reviewing and assessing the performance of the study's operations. The DSMB will convene with the investigators at least semi-annually to review study progress and provide objective recommendations, as appropriate, with respect to:

- Determination of any actions to be taken in response to AEs and SAEs reported during the study;
- Reports related to study operations and the quality of the data;
- Consideration of early termination of the study because of treatment safety concerns or inadequate performance;
- Modifications in the study protocol concerning recruitment, participant retention, data quality, outcome assessment, statistical analysis, or general trial operations.

At the end of each meeting, DSMB members will make a recommendation regarding the continuation of the trial and the date and format of the next meeting. The DSMB's findings and recommendations will be documented in the meeting minutes and transmitted to the

Investigators for their information and action, and will be incorporated into the annual Status Reports to the IRB.

Safety monitoring

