Project staff will be trained to identify and report all potential AEs. To ensure unbiased determination across treatment arms, we will systematically identify AEs by query of the EHR and/or patients at each scheduled data collection time-point. AEs discovered will be investigated and reported to the IRB and DSMB according to required timelines. The DSMB may request additional information if it deems additional deliberation is warranted. The project director and/or analyst will prepare a statistical summary of the numbers and types of all AEs (serious or not), by unidentified treatment arms, for the investigators and the DSMB on a quarterly basis. At the discretion of the DSMB, the Chair may request unblinded results in order to determine the nature and extent of effect of the experimental intervention. Should the DSMB make this request, it will be fulfilled following a procedure that will maintain blinding of the investigators and the staff involved in follow-up data collection and analysis. If, at any time, the investigators believe they are seeing an unexpected increase in AEs that is a cause of concern, this will be specifically brought to the attention of the DSMB and their advice will be sought. This systematic, non-biased monitoring process will ensure that any group disparities will be effectively addressed.

References

1. Cella, D., et al., *What is a clinically meaningful change on the Functional Assessment of Cancer Therapy–Lung (FACT-L) Questionnaire?: Results from Eastern Cooperative Oncology Group (ECOG) Study 5592*. Journal of clinical epidemiology, 2002. **55**(3): p. 285-295.
2. Temel, J.S., et al., *Early palliative care for patients with metastatic non–small-cell lung cancer*. New England Journal of Medicine, 2010. **363**(8): p. 733-742.
3. Friedman, L.M., et al., *Fundamentals of clinical trials*. Vol. 4. 2010: Springer.
4. Borm, G.F., J. Fransen, and W.A. Lemmens, *A simple sample size formula for analysis of covariance in randomized clinical trials*. Journal of clinical epidemiology, 2007. **60**(12): p. 1234-1238.
5. Schafer, J.L., *Multiple imputation: a primer*. Statistical methods in medical research, 1999. **8**(1): p. 3-15.
6. Hollander, M., D.A. Wolfe, and E. Chicken, *Nonparametric statistical methods*. 2013: John Wiley & Sons.

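### The adverse event query rule does not secure the complete, arm-comparable ascertainment that the plan claims for it

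*Combined protocol and SAP*

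**What the plan says.** Section G (Safety monitoring) sets the AE rule: "we will systematically identify AEs by query of the EHR and/or patients at each scheduled data collection time-point". It gives unbiased determination across arms as the purpose and closes by describing the process as systematic and free of bias. Project staff are also trained to report any potential AE. The resulting counts, covering AEs of every seriousness, are tabulated "by unidentified treatment arms, for the investigators and the DSMB on a quarterly basis".

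Other provisions bear on how that rule would work:

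- Section B (Measures): "Outcome measures will be collected on all enrolled participants by a research coordinator at baseline and the final visit".
- Section B (Identification and recruitment process): a payment falls due "after completing 8 weeks in the study". No assessment is described at that point.
- Section F (Secondary Aims, aim 4): referrals to interdisciplinary services "will be monitored on a monthly basis for all enrolled subjects". Admissions, ED visits and survival status come from a CDW extraction at the end of the three-year study period.
- Section G (Data and Safety Monitoring Board): during questionnaires, and also "during the intervention telephone calls, study staff may detect symptoms of depression".
- Section C: the study nurse enters research notes in CPRS, where providers can read them.
- Section D: the DSMB monitors deaths, hospitalizations and ER visits. No method or interval is given.
- Section G (DSMB Role): "The DSMB will convene with the investigators at least semi-annually to review study progress".

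**The concern.** The plan specifies the output, a quarterly by-arm AE table, but not an input that would make the table complete and comparable. Three features of the rule cause this.

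- **Timing.** The query is tied to data collection time-points, and only two are defined for patient assessments. No interval is set for querying records.
- **Source.** The and/or wording allows records for one patient, an interview for another and both for a third. It does not oblige anyone to search the record of a patient who never reaches the final visit.
- **Contact.** Staff who speak to intervention patients by telephone also report AEs. The plan describes no matching calls to control patients.

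At stake is the DSMB's ability to compare arms. Section D sets no formal stopping rules and relies on the board's judgement, including about AEs reasonably attributable to participation. Under-recording in patients who leave early could hide a real difference. Extra contact in one arm could create an apparent one.

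**Working it through.** **Step 1. The plan's own figure.** Section A gives d = 0.45, two-tailed alpha 0.05, 80% power, ρ = 0.5 and 15% attrition.

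- n = 2(1.960 + 0.842)² / 0.45² = 77.52 per arm
- n_final = 77.52 × (1 − 0.5²) / (1 − 0.15) = 68.40, rounded up to 69 per arm, or 138 in total

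This matches the stated 138. The 15% is therefore already built into the enrolled number, and the AE point does not alter the sample size.

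**Step 2. Patients who may lack a final interview.**

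- 0.15 × 138 = 20.7, about 21 patients
- 0.15 × 69 = 10.35, about 10 per arm

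This assumes that attrition means no final visit. It is a measure of scale for the patient interview only. It does not count patients whose records go unsearched, and the plan does not say how many of them would be deaths.

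**Step 3. Scheduled looks at the patient.** Two assessments are defined. The baseline one cannot capture events after randomization, so one useful scheduled interview remains per patient, and none for a patient who leaves before it.

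**Step 4. Sources set against the quarterly table.**

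| Source | Applies to | Timing stated | Can feed a quarterly AE table? |
|---|---|---|---|
| Patient interview | Those reaching the final visit | Baseline, final visit | Once per patient after randomization |
| EHR query | Optional (and/or) | Scheduled time-points, none named for records | Not assured |
| Referral monitoring | All enrolled | Monthly | Yes in timing, but covers referrals, not AEs |
| CDW extraction | All enrolled | End of study period (3 years) | No |
| DSMB monitoring of deaths, hospitalizations, ER visits | All enrolled | Not stated | Possibly, for those events; method not given |
| Staff reports, including from intervention calls | More contact in one arm | As they arise | Yes, but not equally by arm |

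No row is mandatory, at least quarterly, equal in both arms and concerned with AEs generally.

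**Step 5. Delay.** A quarter is 52/4 = 13 weeks. An event that waits w weeks for the final interview is certain to span a quarterly summary only if w is 13 or more; below that the chance is about w/13 (for example 8/13 = 62% at 8 weeks). The largest possible w is the baseline-to-final interval, which the plan does not state. The order of the payments suggests that it exceeds 8 weeks, but that is an inference. The delay therefore cannot be calculated, and an EHR query run between visits would shorten it.

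**Step 6. Unequal detection.** The call route is documented for depression and suicidal ideation. Events of that kind would tend to be recorded more often in the intervention arm. The documents give neither event rates nor call frequency, so the size cannot be computed. If the study nurse's CPRS notes record intervention contacts, the same imbalance could enter through the EHR query. The documents do not say whose contacts the notes cover, so this too is an inference.

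**The case against.** The best reply is that the plan has more routes to safety information than the query sentence suggests. The DSMB monitors deaths, hospitalizations and ER visits. Discovered AEs go to the IRB and DSMB on required timelines without waiting for the quarterly table, and investigators may raise an unexpected increase at any time. An EHR query needs no living or responsive participant. The phrase about scheduled time-points need not mean surveys alone, and quarterly summaries sit naturally with recurring ascertainment. The trial tests no investigational drug or device, serious events are expected from the disease, and the pilot reported no unanticipated serious events due to participation.

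Much of this stands, and it rules out several stronger readings that a reader might infer:

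- That AEs are looked for only twice, or that patients who die or withdraw are never checked again. This holds for scheduled direct questioning, not for records.
- That the quarterly table is the trial's only safety signal. Sections D and G give others.
- That about 21 patients have no AE query after baseline. The figure bears only on the final interview.
- That the intervention arm has a documented advantage in detecting all AEs. The text names depression and suicidal ideation, and names the questionnaires, given in both arms, as a route as well. Deaths, admissions and ER visits can be found in records in either arm.

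What the reply does not supply is a rule. None of these routes states a method and interval for finding AEs alike in both arms. That an EHR query could cover a patient who withdrew does not mean that the plan requires it. Low expected risk bears on how much effort is proportionate, but the plan itself promises unbiased determination and sends the DSMB a by-arm table of all AEs.

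**Conclusion.** The concern holds in a limited form. Followed as written, the rule permits AE ascertainment that is incomplete for patients who leave early, varies in source between patients, and mixes commonly ascertained events with events noticed on calls described for one arm. The exposure is mainly the completeness and comparability of the quarterly by-arm table, above all for non-fatal events that do not lead to a hospital or ER contact.

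The only size that can be given is about 21 of 138 patients (about 10 per arm) who may lack a final interview. It rests on the plan's 15% attrition and on equating attrition with a missed final visit. The tilt from extra contact is plausible in direction but unquantified.

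A reader might also conclude that harms will surface late. The documents do not show this, because neither the final-visit week nor the dates of any EHR query are stated. The sample size and the primary analysis are unaffected. The change is worth making, but the point does not show that the trial is unsafe.

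**What to change.** Amend the query sentence in section G (Safety monitoring) as follows.

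1. Require an EHR query for AEs in every randomized patient in both arms, on a fixed calendar at least as frequent as the quarterly summary. The monthly referral monitoring in section F is a convenient vehicle.
2. Continue the query to the planned end of follow-up or death, whether or not the final survey is completed.
3. Record the source of each AE: EHR query, survey contact or intervention call.
4. Base the between-arm DSMB table on events from this common query, excluding events known only from the study nurse's research notes in CPRS. Without that exclusion the contact imbalance could return through the record.
5. List events known only from intervention calls separately, so that the DSMB still sees them.

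The cost is one revised paragraph, a source field on the AE form and modest extra chart-review time. One limit remains: events that never reach the chart will be missing from the between-arm table, but the same rule will then apply to both arms.
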